#### **Exclusion Criteria:**

- Tumor in functionally eloquent cortex that precludes maximal surgical resection
- Severe renal dysfunction
- Preoperative serum creatinine level > than normal range and GFR < 30.

- Severe liver dysfunction
- History of asthma or pulmonary spasm
- Known allergy to sodium fluorescein or any other contrast dye
- Previous administration of sodium fluorescein within the last 72 hours
- Pregnant or nursing mother
- Other unspecified reasons that, in the opinion of the investigator, make the subject unsuitable for enrollment.
- Tumors with primary differential diagnosis not included in the inclusion groups

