# C. Study Design and Research Methods

## Study Design:

This study will be a prospective non-randomized cohort study with patients presenting to Children's Hospital Colorado for resection of a central nervous system tumor. Due to heterogeneity of the pediatric central nervous system tumors and the evidence available, we will have a planned initial cohort (first phase) that will include tumor pathology that will allow us to test the feasibility of the study and the preliminary activity of fluorescein in the pediatric population. After completion of this initial cohort, we will expand our study to include tumors that are more specific to the pediatric population.

Currently, there exist many tumor types where there is robust literature on the use of fluorescein [3,4,6-15,21-26,27-29]. We plan to enroll patients based on a phased system and after completion of the first phase, we will perform a safety analysis as outlined below.

[name]: 18-0242 Page 3 Version: 07/03/2019

After safety analysis is completed, we will either proceed to the next phase, or in the event there is a safety concern, the DSMC will terminate our study. Terms for termination are detailed below.

Enrollment of ten patients is planned for each tumor type in each of the phases. The phases are designed to assess patients where evidence is available and proceed to tumor types where pediatric evidence is limited and the tumors are more unique to the pediatric population. This will allow us to safely assess patients and allow us to expand our trial in a controlled fashion. After completion of each phase of enrollment, we will continue enrolling the prior phase patients for a maximal total of 10 patients per each pathology group. Thus, maximal enrollment will be 20 patients for the first phase pathologies and 30 patients for the second phase pathologies, for a total enrollment of 50 treated patients and 150 historical controls

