#### Research Methods:

Study Recruitment: The primary neurosurgeons who will perform the resections will be investigators on the study and will identify eligible patients from their established practice. At the time surgical intervention is recommended, they will inform patients and parents/guardians of the existence of the study. Only those subjects with a clinical relationship with the study investigators will be recruited.

Informed Consent and Assent: Patients (and parents/guardians of child patients) will be informed of the risks and possible benefits of the study, and informed consent will be obtained before any research procedures are initiated. Those who are interested in participating in the study will be informed of the study details by a member of the research team. Ample time will be provided to answer any questions and concerns regarding the study during the consenting process and patients will be given the option to take the consent form home to review. Additionally, patients will be provided with contact information in the event that questions should arise. Patients who undergo emergent surgery in which there is not sufficient time to obtain informed consent will be excluded from the study. In children 7-17 years, informed assent will also be obtained. Patients 18 years and older will consent for themselves.

Eligibility Assessment: All inclusion/exclusion factors that result from procedures (imaging or laboratory tests) will already be clinically documented as part of the standard of care, so will be evaluated via chart review for the study. There are no study-specific screening tests or screening procedures.

The exclusion criteria "preoperative serum creatinine level > normal range and GFR < 30" will be evaluated through chart review (creatinine level is included in standard of care preoperative lab results). The reference ranges used by Children's Hospital Colorado's clinical lab will be used to determine the normal range based on the patient's age and gender. If a patient's serum creatinine is greater than the normal range, GFR will be calculated using the following equation. If the GFR is < 30, the patient will be excluded.

Table 2: GFR Calculation

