Given this, we propose a 3:1 ratio of historical controls to fluorescein treated patients to match tumor location and histology. 150 historical controls will be pulled from the last ten years of Children's Hospital patients and matched to the 50 fluorescein treated cases on lesion location and pathology. This 3:1 ratio will strengthen our ability to objectively assess for adverse events related to sodium fluorescein as well as our extent of tumor resection analysis. Importantly, historical controls undergo stereotactic-guided tumor resection in a similar fashion to patients undergoing fluorescein administrations as outlined in our protocol.

All patients who undergo sodium fluorescein-aided resection will also have neuropathological analysis. We will analyze correlation of fluorescein staining to histopathology. Tissue obtained during the time of surgery will be used to correlate fluorescein staining to histopathological diagnosis. This data will be used to calculate sensitivity and specificity of fluorescein staining for tumors. Pre- and post-operative imaging will be used to assess the degree of the extent of resection in intraparenchymal tumors. Data collected from post-operative follow-up will be used to assess for potential complications/adverse reactions associated with sodium fluorescein administration.

For data analysis, extent of tumor resection will be compared as a continuous value across groups using a parametric ANOVA. Further calculations, such as sensitivity, specificity and positive predictive value will be calculated by contingency tables. Additionally, since group membership is not random we will run an adjusted analysis predicting the likelihood of tumor resection as a continuous outcome adjusting for demographic and co-morbidity factors. Significance will be assigned at p < 0.05.

Furthermore, adverse reactions and population/demographic data will be characterized using relative risk and odds ratios. Overall survival and progression free survival analysis will be characterized using Kaplan-Meier curves and compared across groups using a log rank test.

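### Surgeon-led, discretionary and unlogged enrolment, with exclusions not stated to apply to the historical controls, allows selection on expected resectability that the plan could not detect

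*Combined protocol and SAP*

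**What the plan says.** All references are to the combined protocol and SAP.

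- **Design.** Section IV.C (Study Design): "This study will be a prospective non-randomized cohort study", planned "for a total enrollment of 50 treated patients and 150 historical controls", with at most 10 treated patients per pathology group.
- **Who finds the patients.** Section IV.C (Study Recruitment): "The primary neurosurgeons who will perform the resections will be investigators on the study and will identify eligible patients from their established practice". It adds: "Only those subjects with a clinical relationship with the study investigators will be recruited".
- **Exclusions.** Section IV.B lists "Other unspecified reasons that, in the opinion of the investigator, make the subject unsuitable for enrollment", and also "Tumor in functionally eloquent cortex that precludes maximal surgical resection".
- **Who ends the resection.** Section IV.C (Tumor Resection) leaves it to the primary surgeon to judge when the surgical goal has been met.
- **Controls.** Section IV.F draws 150 patients from the last ten years at the same hospital, "matched to the 50 fluorescein treated cases on lesion location and pathology". It does not say how they are chosen among those who match, or whether the section IV.B exclusions apply to them.
- **Analysis.** Section IV.F compares extent of resection as a continuous value by ANOVA. Because group membership is not random, it adds an analysis adjusted for demographic and co-morbidity factors. Tumour size and preoperative resectability are not named.
- **Records.** No section requires consecutive approach, a screening log or reasons for non-enrolment. The six-monthly report in section IV.H covers current numbers, toxicity, deviations and amendments, but not screening.

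**The concern.** An investigator-discretion clause does little harm to a randomised comparison, because selection happens before allocation and affects both arms alike. Here the comparison is with past patients, and the discretion is exercised prospectively on those about to be treated. The person exercising it has the preoperative imaging, performs the operation and decides when it is finished. A preoperative view of how much tumour can be removed is close to a forecast of the primary outcome.

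The eloquent-cortex criterion works through the same channel, and in writing: it removes treated candidates because maximal resection is not expected. If controls are drawn without that criterion, the two groups differ on expected resectability before any fluorescein is given.

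At stake is whether a difference in mean extent of resection can be read as an effect of fluorescein. Without a record of who was eligible and not enrolled, nobody could later show that selection did not produce it.

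**Working it through.** **1. The plan's own figure.** Section IV.F, Table 3: difference 16 points, SD 25, alpha 0.05. A two-sided, two-group t-test (equivalent to the two-group ANOVA) with equal arms needs 31.13, 39.31 and 52.29 per arm for 70%, 80% and 90% power. Rounded up these are 32, 40 and 53, giving totals of 64, 80 and 106, exactly as in Table 3. The SD and difference can therefore be carried forward.

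**2. Precision of the planned comparison.** With 50 v 150:

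SE = 25 × √(1/50 + 1/150) = 4.08 points.

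With 198 degrees of freedom, an observed difference of about 8.05 points reaches p < 0.05.

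**3. Shift from selective enrolment.** Suppose the fraction q of eligible patients forecast to do worst is not enrolled, and the forecast correlates ρ with the actual extent of resection. On a normal approximation:

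shift = ρ × SD × φ(z_q) / (1 − q).

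The documents give neither q nor ρ, so both are assumptions.

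- q = 0.10: φ(z) = 0.1755, and 0.1755/0.9 = 0.195. At ρ = 0.5, 0.5 × 25 × 0.195 = 2.44 points; 2.44/16 = 15%.
- q = 0.20: φ(z) = 0.2800, and 0.2800/0.8 = 0.350. At ρ = 0.5, 0.5 × 25 × 0.350 = 4.37 points; 4.37/16 = 27%.

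**4. Effect on the test when fluorescein does nothing.** Noncentral t with 198 df, noncentrality = shift/SE, SD held at 25:

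| Not enrolled (q) | ρ | Shift (points) | False-positive rate |
|---|---|---|---|
| 10% | 0.3 | 1.5 | 6.5% |
| 10% | 0.5 | 2.4 | 9.1% |
| 10% | 0.7 | 3.4 | 13% |
| 20% | 0.3 | 2.6 | 9.8% |
| 20% | 0.5 | 4.4 | 19% |
| 20% | 0.7 | 6.1 | 32% |

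The nominal rate is 5%.

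**5. Sensitivity.** The shift is proportional to the SD. At ρ = 0.5 it is 0.0975 SD (q = 0.10) or 0.175 SD (q = 0.20). Matching on location and pathology leaves only variation within strata, so the relevant SD, and with it the shift, may be below the values above. The table also treats controls as unselected on resectability. Selecting them in the same way would shrink the difference.

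**6. Safeguards set against the channel.** Matching removes the part of expected resectability that follows location and pathology, but not differences between tumours alike on both. The adjusted analysis names demographics and co-morbidity only. Blinding the neuroradiologists (section IV.C, Imaging) protects the reading of scans, not the choice of patients.

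**The case against.** The strongest reply is that the clause is a standard catch-all that does not mention resectability. Families decide on consent, and exclusion factors that come from imaging or laboratory tests are checked by chart review. Eligible patients are scarce enough that section IV.F calls a randomised trial infeasible, so surgeons have reason not to discard candidates. Section IV.E acknowledges the lack of randomisation and calls the study a pilot. Logs are often kept without being written into a protocol.

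Much of this stands as context. It shows that selection need not happen, not that the plan would prevent or reveal it.

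Four stronger readings are tempting, and the documents do not support them:

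- *The controls are an unpicked series.* Section IV.F gives no rule for choosing them, and they may be selected in some other way. All that can be said is that they are not stated to pass the same exclusions or the same prospective judgement.
- *Matching does nothing.* It removes whatever part of expected resectability follows location and pathology.
- *The bias could be over half the planning difference.* Leaving out the worst 20% with perfect foresight gives 25 × 0.350 = 8.75 points, or 55% of 16. Nothing in the documents supports perfect foresight. At ρ = 0.5 the shift stays below the 8.05 points needed for significance, so it would not usually produce a positive result alone.
- *The bias must favour fluorescein.* Surgeons might instead prefer difficult tumours for the new tool, which would hide a benefit.

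**Conclusion.** The point holds as a design weakness. In this comparison with historical controls, the plan lets the operating surgeon's preoperative judgement affect who is treated, through an open-ended exclusion and through a written criterion tied to the endpoint. It does not say that either applies to controls. The planned matching and adjustment deal with this only in part, and the records it requires would not show it.

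The size cannot be derived from the documents. The illustration of 2.4–4.4 points, with a false-positive rate of about 9–19% instead of 5%, rests on an SD of 25, normality, 10–20% not enrolled, a forecast correlation of 0.5 and controls not selected in the same way. It shows that modest selection matters, and is not an estimate of what will happen. The documents do not show that selection has occurred or will occur. The absence of a log is judged on the protocol text available, and one may be kept as site practice.

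**What to change.** 1. Restrict the discretionary exclusion to medical or safety reasons unrelated to expected resectability.
2. Offer the study to consecutive eligible patients until each quota of 10 is full.
3. Keep a prospective screening log with a reason for every eligible patient not enrolled, separating family refusals from investigator exclusions. It must be kept as patients present, because reasons cannot be reliably rebuilt later.
4. Apply the same eligibility criteria when drawing the 150 controls, including the eloquent-cortex criterion judged from preoperative imaging.
5. With IRB agreement, report extent of resection in eligible patients not enrolled, from their standard-of-care scans, beside the treated and control groups.

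The cost is a log, some chart and image review for controls and non-enrolled patients, and slightly less investigator discretion. The planned numbers, the drug administration and the surgery do not change.

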#### Calculation for GFR

$$\mathit{GFR} = \frac{0.41*\mathit{Height\ in\ cm}}{\mathit{Serum\ Creatinine\ in\ mg/dL}}$$

The exclusion criteria "pregnant or nursing mother" will be evaluated for females of childbearing potential. We will utilize Children's Hospital Colorado's perioperative definition of childbearing potential as females who have reached menarche or are 12 years of age or older. Pregnancy testing is standard of care for these patients and pregnancy test results will be evaluated through chart review.

[name]: 18-0242 Page 5 Version: 07/03/2019

<sup>1See Follow Up section below for more detail

Pre-operative Evaluation: A standard of care neurosurgical assessment will occur at admission: standard clinical evaluation for tumor including pertinent history, physical and neurologic exam data, laboratory findings, and initial imaging studies will all be documented clinically and recorded via chart review for the study.

Imaging: Patients will have pre- and post-operative imaging in accordance with the standard clinical procedures at Children's Hospital Colorado. Patients in this study will not require any study-specific imaging outside the standard of care. All post-operative images are reviewed by fellowship trained pediatric specific neuroradiologists. Neuroradiologists are not informed on the administration of sodium fluorescein and will conduct review of the post-operative imaging per standard protocol. No imaging evidence of sodium fluorescein is visible on post-operative MR or CT imaging and the independent neuroradiologist is blinded to the operative course of the patient.

Sodium Fluorescein Administration: Patients enrolled in this study will receive 3 mg/kg sodium fluorescein following induction of anesthesia by administration into a peripheral venous line over 10 seconds. This dose has been previously reported for use in a pediatric population and has been studied in adult tumor population [15]. Previous studies have used doses ranging from 500mg standing to 20mg/kg with minimal side effects [7]. The FDA-approved dosage for children is 7.7 mg/kg intravenously. A lower dose and earlier administration reduces the incidence of fluorescent contamination of normal brain. Furthermore, the advent of new neurosurgical microscopes with fluorescein filters decreases the dosage required to observe fluorescence.

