Tumor Resection: Resection of the lesions will proceed as normal as if sodium fluorescein had never been given. Resection will proceed with the use of a surgical microscope equipped with excitation and barrier filters for monitoring with sufficient fluorescent enhancement and contrast. The surgeon will be capable of switching the filters so as to observe the ordinary microscopic image and the fluorescein image as necessary. This ensures that the safety and normal operating procedure are minimally disturbed during this study.

Fluorescein absorbs at a peak between 465-490 nm which is selected for from the light source by the excitation filter. The barrier filter will only permit fluorescence emitted by sodium fluorescein in the 500-530 nm range to the surgeon's eye. The margins of resection will be based on identifying the fluorescein stained tissue that indicates neoplastic change and breakdown of the blood brain barrier. The resection will be performed piece by piece until the primary surgeon feels that surgical goal is achieved. Samples of fluorescent tissue will be sent to pathology for evaluation of histology.

Utilizing the microscope's internal recording device, we will record or photograph the surgery. When possible, biopsy location will be marked on the patient's preoperative MRI with the neurosurgical navigation device and a screenshot of this localization will be taken from the device system. This will only be possible for intracranial lesion and will not be used for spinal lesions. Images will be stored on a password-protected encrypted computer on the Children's Hospital Colorado server and accessible only to the investigators. Biopsies will be sent to pathology for diagnosis as is customary in all tumor resections, and diagnosis will be followed up in the patient's medical record by authorized study personnel. Fluorescein staining will be correlated with biopsies/pathological samples based on samples collected per standard of care. Official pathology reports will be used to determine pathological correlations with fluorescein staining.

Follow-Up: A neurosurgical assessment will occur post-operatively prior to discharge, as well as at standard of care outpatient follow-up clinic visits that take place between discharge and Month 2 post-surgery. These clinic visits typically occur at one week (for incision check) and one month post- surgery. Standard clinical evaluation for tumor includes pertinent history,

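### Historical controls are not held to the pre-operative diagnosis rule that treated patients must meet, which can bias the comparison of extent of resection

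*Combined protocol and SAP*

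**What the plan says.** **Treated patients.** Section IV.B names two tumour types for the first phase and three for the second, and excludes "Tumors with primary differential diagnosis not included in the inclusion groups". Under Section IV.C (Research Methods), "informed consent will be obtained before any research procedures are initiated". Dosing comes at the start of the operation: "Patients enrolled in this study will receive 3 mg/kg sodium fluorescein following induction of anesthesia" (Section IV.C, Sodium Fluorescein Administration). The tissue diagnosis comes from that operation: "Biopsies will be sent to pathology for diagnosis as is customary in all tumor resections" (Section IV.C, Tumor Resection).

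**Controls.** Section IV.F states: "we propose a 3:1 ratio of historical controls to fluorescein treated patients to match tumor location and histology". They come from the hospital's patients of the past ten years and are "matched to the 50 fluorescein treated cases on lesion location and pathology". Nothing there or elsewhere says that controls must satisfy the Section IV.B diagnosis criterion.

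**Outcome and adjustment.** The primary outcome is extent of resection on imaging (Section IV.A). Surgery ends when the surgeon judges that its goal has been met (Section IV.C, Tumor Resection). The adjusted analysis in Section IV.F names demographic and co-morbidity factors. It names neither tumour group nor pre-operative diagnosis.

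**The concern.** The two arms pass through different entry rules. One is filled on what the tumour was thought to be before surgery. The other is filled, on the natural reading of pathology and histology for a past surgical patient, on what the tumour proved to be. A tumour of a listed histology whose leading pre-operative diagnosis was something else is barred from treatment but available as a control.

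Such tumours may have looked atypical, or been approached with a different goal, and the goal helps to decide how much is removed. If their extent of resection differs from that of tumours recognised before surgery, the treated-versus-control difference carries that gap as well as any effect of fluorescein. Matching on histology and location cannot correct it, because the difference lies within a histology, and the named covariates do not capture it.

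**Working it through.** **1. The plan's own figure.** Inputs from Section IV.F: difference 93.1 − 77.1 = 16 points, SD 25, alpha 0.05. A two-group ANOVA with equal groups is a two-sided t test with standardised effect 16/25 = 0.64. It needs 32, 40 and 53 per group for 70%, 80% and 90% power, so 64, 80 and 106 in total. Table 3 is reproduced exactly. The planned 50 versus 150 has 97.4% power. Precision is therefore not the problem, and adding controls does not reduce a bias.

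**2. Who can enter each arm.**

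| Leading pre-operative diagnosis | Final histology | Can be treated? | Can be a control? |
|---|---|---|---|
| Listed | Listed | Yes | Yes |
| Listed | Off-list | Yes | Yes, if matched to such a treated case |
| Off-list | Listed | No | Yes; nothing prevents it |
| Off-list | Off-list | No | Yes, if matched to a treated case of that histology |

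The asymmetry is in the last two rows. In the fourth row, a treated child whose tumour proves off-list may be matched to controls whose tumours were correctly recognised as off-list before surgery.

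**3. Size, under assumed inputs.** Let q be the share of controls whose leading pre-operative diagnosis would have excluded them, and D the gap in mean extent of resection between them and the other controls. The comparison shifts by b = q × D. The documents give neither input, so both ranges below are assumptions. Note that q is a share of controls; it is not the misdiagnosis rate among treated patients.

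The standard error is 25 × √(1/50 + 1/150) = 4.08 points. By the normal approximation:

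- type I error if the shift favours fluorescein = 1 − Φ(1.96 − b/4.08) + Φ(−1.96 − b/4.08);
- power if it works against fluorescein = Φ((16 − b)/4.08 − 1.96).

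| q and D giving this shift | b (points) | b/16 | Type I error | Power |
|---|---|---|---|---|
| 5%, 5 | 0.25 | 2% | 5.0% | 97.1% |
| 5%, 10 or 10%, 5 | 0.5 | 3% | 5.2% | 96.7% |
| 5%, 20 or 10%, 10 or 20%, 5 | 1.0 | 6% | 5.7% | 95.7% |
| 10%, 20 or 20%, 10 | 2.0 | 13% | 7.8% | 92.9% |
| 20%, 20 | 4.0 | 25% | 16.5% | 83.6% |

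**4. Spinal group.** Contrast-enhancing spinal tumours are defined by imaging and location, so the point largely does not apply to them. At 3:1 they account for 30 of the 150 controls. If q applies only to the other 120, each shift is multiplied by 120/150 = 0.8, giving a range of 0.2 to 3.2 points. At 3.2 points the type I error is 12.3%, or the power 88.0%.

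**The case against.** The strongest reply is that controls follow the cases. They are matched to the treated patients and are not drawn separately from five named histologies. A reader might infer that misdiagnosed tumours appear only in the treated arm. The text does not support that: a treated child with an unexpected histology would naturally receive controls of the same histology, and the tumour-mix part of any bias is then about zero. This stands, but it does not touch selection on pre-operative diagnosis within a histology.

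Two other strong readings also fail:

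- **The quotas of ten are not of the named tumours.** Section IV.C plans ten per tumour type and enrolment "for a maximal total of 10 patients per each pathology group". That is a cap, and whether it is counted on presumed or final diagnosis is ambiguous. It is not shown to be wrong.
- **Off-list patients fall out of the first-phase safety review.** Section IV.G has adverse events after fluorescein recorded without regard to histology. Section IV.H gives the monitoring committee continuing review of all serious events, and the first-phase review is not limited to confirmed histologies.

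It is also fair to say that final pathology is inferred from the words pathology and histology, and that some patients may have earlier histology, since re-enrolment for further resection is allowed. Section IV.F adds that controls had similar stereotactic-guided surgery. That speaks to technique and leaves the presumed diagnosis open. Finally, no document supports a direction of bias, and q and D are assumed.

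**Conclusion.** The concern holds in limited form. Treated patients are screened on the leading pre-operative diagnosis, no such screen is stated for controls, and histology matching cannot make up for it. Extent of resection can be biased as a result, in either direction.

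The size cannot be established from the documents. Under the assumed ranges it is 0.25 to 4 points, or 0.2 to 3.2 points once the spinal group is set aside. That is small beside the planned 16 points unless such controls are common and their resections differ strongly. No stated figure in the plan is wrong. The change is worth making because it is specific and cheap, and because neither the matching nor the named covariates address this source of bias.

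**What to change.** - **Common entry rule.** Require each candidate control to meet the Section IV.B differential-diagnosis criterion, judged from the pre-operative radiology report or neurosurgical note. Then match on location and histology as planned. Report how many candidates this removes, which supplies the missing rate.
- **Primary analysis set.** State that every dosed patient stays in the primary extent-of-resection analysis, whatever the final histology.
- **Sensitivity analysis.** Repeat the comparison in cases and controls whose pre-operative and final diagnoses agree. If this removed 10% or 20% of each arm (assumed), 45 versus 135 or 40 versus 120 would still have 95.9% or 93.6% power for 16 points.

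Replacing histology matching with matching on pre-operative diagnosis is not needed, and could leave the arms unequal in final histology.

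The cost is protocol wording and extra chart reading, for patients whose pre-operative imaging must be retrieved anyway for the primary outcome. The control pool shrinks somewhat, and 3:1 may not be reached for rare histologies. A fall to 2:1 overall would matter little for power: with 50 versus 100 the standard error is 25 × √(1/50 + 1/100) = 4.33, and Φ(16/4.33 − 1.96) is about 96%.
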